8.3.2 Secondary Endpoints

- Change in NT-proBNP from baseline to Hour 24, 48, 72, 120 or discharge (whichever comes first), and at Day 32
- Change in patient-reported resting dyspnea from baseline through Hour 72, as measured by the area under the curve (AUC) of the 11-point Numerical Rating Scale (NRS) obtained at baseline, and Hours 6, 12, 24, 48, and 72

8.3.4 Safety Endpoints.

Safety endpoints consist of the following:

- The incidence of symptomatic hypotension up to 6 hours after the end of study drug infusion
- The incidence of SBP < 90 mm Hg (confirmed by a repeated value)
- Change in Troponin T from baseline to Hour 24, 48, and 72
- Percentage of subjects who have died (all- cause and CV related)

Additionally, the percentage of subjects with discontinuation due to symptomatic hypotension, as well as percentage of subjects with down-titrations, interruptions or discontinuations as a result of low blood pressure, either protocol specified clinically relevant hypotension, or asymptomatic decreases will be assessed. Other safety endpoints include the incidence of Adverse Events and Marked Laboratory Abnormalities, changes from baseline in vital signs, ECGs, physical measurements and laboratory assessments through Hour 120 or discharge, whichever comes first. The incidence of Serious Adverse Events will be assessed though Day 32.

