8.4.2.2 Secondary Endpoint Analyses

NT-proBNP will be summarized descriptively by treatment for each time point, as well as change from baseline.

Analyses for changes from baseline in the resting dyspnea as measured by the 11-point NRS will be done using a longitudinal repeated measures model, with baseline value and region as covariates. A trapezoidal rule will be applied to calculate AUC using model-estimated values from the time points. Missing values for the dyspnea NRS will not be imputed, except if a NRS cannot be obtained because the subject has died or is physically unable to complete the form. In these cases, a worst score imputation will be used for that time point.

[REDACTED]

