4.1.2 Secondary Efficacy Endpoints

Secondary endpoints include the following:

- Change in NT-proBNP from baseline to Hour 24, 48, 72, 120 or discharge (whichever comes first), and at Day 32
- Change in patient-reported resting dyspnea from baseline through Hour 72, as measured by the area under the curve (AUC) of the 11-point Numerical Rating Scale (NRS) obtained at baseline, and Hours 6, 12, 24, 48, and 72

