7.1 General Methods

Results from Part I (Cohort 1) and Part II (Cohort 2) will be presented separately, unless otherwise noted.

Except as noted otherwise, descriptive summaries will be presented for continuous variables using number of subjects (N), mean, standard deviation (SD), median, minimum and maximum. Descriptive summaries for categorical variables will utilize counts and percentages. Several analyses noted in subsequent sections will present 95% confidence intervals (CIs), but no pre-specified significance testing will be included.

Adverse events and medical history will be coded according to the most recent Medical Dictionary for Regulatory Activities (MedDRA) version. Previous and concomitant medications will be coded using the WHO Drug Dictionary.

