7.5.2 Secondary Efficacy Analysis

NT-proBNP will be summarized descriptively for all treated subjects by treatment for each time point, as well as change from baseline. Geometric mean and coefficient of variation (%CV) will also be presented for the original values and percent of baseline.

The NRS is an ordinal scale of 0 to 10. A score of 0 represents “I am not breathless at all” and 10 represents “I am the most breathless I can possibly imagine”.

To incorporate the correlations among NRS assessments at different time points and an appropriate representation of effect of baseline assessments, the change from baseline at time point t (Hour 24, 48, and 72) in NRS assessments will be analyzed using a longitudinal repeated measures method. The model will include treatment, region and time as fixed effects and baseline value as covariate. Furthermore, interaction terms of time by treatment, time by region and time by baseline value will be included. An unstructured variance-covariance matrix for the NRS assessments within same subject will be used (Autoregressive structure will be used if the model does not converge with unstructured matrix.). The SAS[®] procedure PROC MIXED will be used.

After obtaining the estimates of mean change from baseline at time point t in NRS assessments, the mean change in AUC within a treatment group or difference in mean change in AUC between treatment groups will be estimated within the framework of the mixed model, using the formula based on the Trapezoidal rule:

$$\Delta AUC = \sum_{i=1}^3 (t_{i+1} - t_i) \frac{y_{t_{i+1}} + y_{t_i}}{2}$$

where y_{t_i} is the estimate of mean change from baseline at target time t_i in a treatment group for estimation of mean change in AUC within treatment group, and for estimation of difference in change in AUC between treatment groups, y_{t_i} is the estimate of mean difference between treatment groups in change from baseline at target time t_i . The variability of ΔAUC will also be estimated

within the framework of the mixed model in SAS using variability from terms used in the ESTIMATE statement.

Missing values for the dyspnea NRS will only be imputed if a NRS cannot be obtained because the subject has died or is physically unable to complete the form. In these cases, a worst score (i.e. 10) imputation will be used for that time point. Missing values for subjects who are discharged prior to Hour 120 will not be imputed.

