7.6.2.9 Oxygen Saturation

Oxygen Saturation will be summarized descriptively for all treated subjects by treatment for each time point as well as change from baseline.

7.7.1 7-Point Likert Scale

Both the percentage of subjects reporting moderate or markedly improved resting dyspnea and percentage of subjects reporting moderate or marked improvement using the patient global assessment on a 7-point Likert scale will be analyzed and presented in the same manner as the primary endpoint at Hours 6, 12, and 24. Missing values for the Likert scale at Hours 6, 12, and 24 will only be imputed, if a score cannot be obtained because the subject has died or is physically unable to complete the form. In these cases, a worst score imputation (i.e. -3) will be used for that time point.

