8.3 Hour Ranges for Analysis of Time Points

Subjects do not always adhere strictly to the visit schedule timing in the protocol. The hour ranges for the analyses of dyspnea measured by 11-point NRS and 7-point Likert scale and patient global assessment (PGA) measured by 7-point Likert scale are defined in Table 8.3-1. The hour ranges for the analyses of laboratory ECG are defined in Table 8.3-2 and 8.3-3, respectively. The hour ranges for the analyses of assessments measured at Hour 24, 48, 72, 96, and 120 (including respiratory rate and temperature) are defined in Table 8.3.4.

Table 8.3-1: Hour Ranges for Analyses of Dyspnea Measured by 11-point NRS and 7-point Likert Scale and PGA Measured by 7-point Likert Scale

Nominal Visit	Target Hour	Hour Ranges
Baseline	Pre-dose	Randomization to \leq Hour 0
Hour 6	Start of infusion + 6	\geq Hour 3 to < Hour 9
Hour 12	Start of infusion + 12	\geq Hour 9 to < Hour 18
Hour 24	Start of infusion + 24	\geq Hour 18 to < Hour 36
Hour 48	Start of infusion + 48	\geq Hour 36 to < Hour 60
Hour 72	Start of infusion + 72	\geq Hour 60 to < Hour 96
Hour 120	Start of infusion + 120	\geq Hour 96 to \leq Hour 132

Table 8.3-2: Hour Ranges for Analyses of Laboratory Measurements

Nominal Visit	Target Hour	Hour Ranges
Baseline	Pre-dose	Randomization to \leq Hour 0
Hour 24	Start of infusion + 24	\geq Hour 12 to < Hour 36
Hour 48	Start of infusion + 48	\geq Hour 36 to < Hour 60
Hour 72	Start of infusion + 72	\geq Hour 60 to < Hour 96
Hour 120	Start of infusion + 120	\geq Hour 96 to \leq Hour 132

Table 8.3-3: Hour Ranges for Analyses of ECG

Nominal Visit	Target Hour	Hour Ranges
Baseline	Pre-dose	Randomization to \leq Hour 0
Hour 48	Start of infusion + 48	\geq Hour 24 to < Hour 60
Hour 72	Start of infusion + 72	\geq Hour 60 to < Hour 96
Hour 120	Start of infusion + 120	\geq Hour 96 to \leq Hour 132

Table 8.3-4: Hour Ranges for Analyses of Respiratory Rate and Temperature

Nominal Visit	Target Hour	Hour Ranges
Baseline	Pre-dose	Randomization to \leq Hour 0
Hour 24	Start of infusion + 24	\geq Hour 12 to < Hour 36
Hour 48	Start of infusion + 48	\geq Hour 36 to < Hour 60
Hour 72	Start of infusion + 72	\geq Hour 60 to < Hour 84
Hour 96	Start of infusion + 96	\geq Hour 84 to < Hour 108
Hour 120	Start of infusion + 120	\geq Hour 108 to \leq Hour 132

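### SAP 7.5.2 computes the dyspnea NRS AUC from Hours 24, 48 and 72 only, whereas the secondary endpoint is defined with Hours 6 and 12 as well

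*SAP*

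**What the plan says.** **Endpoint.** SAP 4.1.2 defines the change in resting dyspnea through Hour 72 as an AUC of the "Numerical Rating Scale (NRS) obtained at baseline, and Hours 6, 12, 24, 48, and 72". Protocol 8.3.2 lists the same times.

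**Protocol analysis.** Protocol 8.4.2.2 says "A trapezoidal rule will be applied to calculate AUC using model-estimated values from the time points". It does not restrict which times are used.

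**SAP analysis.** SAP 7.5.2 says "the change from baseline at time point t (Hour 24, 48, and 72) in NRS assessments will be analyzed" with a longitudinal repeated measures model. It then applies a trapezoidal formula to the estimated mean changes, with the sum running from i = 1 to 3. The times t1 to t4 are not listed beside the formula.

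**Data handling.** The protocol synopsis and Table 5.1-2 schedule the NRS at Hours 6 and 12. SAP 8.3 introduces "The hour ranges for the analyses of dyspnea measured by 11-point NRS and 7-point Likert scale", and Table 8.3-1 gives Hour 6 the window 3 to <9, Hour 12 the window 9 to <18, and Hour 24 the window 18 to <36.

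**Inference.** SAP 7.1 states that "no pre-specified significance testing will be included".

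**The concern.** An endpoint on six times (baseline plus five) needs five trapezoids, and SAP 7.5.2 has three. The two details in that section, the list of hours and the upper limit of the sum, agree with each other, so this does not look like one mistyped number. A programmer who followed 7.5.2 to the letter would leave out Hours 6 and 12 and still label the result as the secondary endpoint.

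Those two assessments are the only NRS data from the first half-day of a 48-hour infusion. Without them, the first 24 hours are replaced by a straight line from zero at baseline to the Hour 24 mean. An early benefit that fades by Hour 24 would be missed, and a benefit that appears only at Hour 24 would be overstated. If the conflict is left until the data are unblinded, there will be two defensible AUCs and a choice between them made with the results in view.

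**Working it through.** **Inputs.** Endpoint times 0, 6, 12, 24, 48, 72 (SAP 4.1.2, protocol 8.3.2). Modelled times 24, 48, 72 and a three-term sum (SAP 7.5.2). The quantity summed is mean change from baseline, or its between-arm difference, so the value at Hour 0 is 0 by construction.

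**Step 1: which grid the SAP formula implies.** {24, 48, 72} gives 2 trapezoids, {0, 24, 48, 72} gives 3, and {0, 6, 12, 24, 48, 72} gives 5. Only baseline plus 24, 48 and 72 matches both the upper limit of 3 and the listed hours. That t1 is Hour 0 is inferred, because the SAP does not say it.

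**Step 2: weights.** Under the trapezoidal rule the weight of an interior time is half the sum of its two adjacent intervals, and the last time gets half the last interval.

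| Hour | Endpoint | SAP 7.5.2 |
|---|---|---|
| 6 | (6+6)/2 = 6 | 0 |
| 12 | (6+12)/2 = 9 | 0 |
| 24 | (12+24)/2 = 18 | (24+24)/2 = 24 |
| 48 | (24+24)/2 = 24 | 24 |
| 72 | 24/2 = 12 | 12 |
| Total | 69 | 60 |

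Hours 6 and 12 carry 15/69 = 21.7% of the post-baseline weight in the endpoint and none in the SAP. Of those 15 units, 6 move to Hour 24, and the net loss is 9/69 = 13%. The windows in Table 8.3-1 do not overlap, so Hour 6 and 12 values cannot enter through Hour 24.

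**Step 3: the difference.** Subtracting the weights gives −6, −9, +6, 0, 0. Hence SAP AUC − endpoint AUC = 6·d24 − 6·d6 − 9·d12. The two agree only when 6·d6 + 9·d12 = 6·d24. Linear onset satisfies this: with d6 = d24/4 and d12 = d24/2, 1.5·d24 + 4.5·d24 = 6·d24.

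**Step 4: illustrative profiles.** The documents give no NRS effect, so these are assumptions (differences in NRS points, AUC in point-hours).

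| Between-arm difference | Endpoint | SAP 7.5.2 |
|---|---|---|
| −1 at every time from Hour 6 | −69 | −60 |
| −1 at Hours 6 and 12 only | −15 | 0 |
| −0.5 at Hours 6 and 12, then −1 | −61.5 | −60 |
| 0 until Hour 24, then −1 | −54 | −60 |
| Linear to −1 at Hour 24, then −1 | −60 | −60 |
| −1 at Hours 48 and 72 only | −36 | −36 |

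**Step 5: precision.** SE = √((2/n)·w′Σw), where w holds the weights and Σ is the covariance of the changes. I take n = 70 per arm (Part II) and assume an SD of change of 2 to 3 points and an exchangeable within-subject correlation of 0.5 to 0.7.

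| Profile | Estimate/SE, endpoint | Estimate/SE, SAP 7.5.2 |
|---|---|---|
| Constant −1 | 2.24 to 3.75 | 2.19 to 3.59 |
| Linear onset, then −1 | 1.95 to 3.26 | 2.19 to 3.59 |

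The endpoint version is 2% to 5% better for a constant effect. The SAP version is 10% to 12% better for linear onset.

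**The case against.** The best defence is that the three-time AUC still covers 0 to 72 hours on a coarser grid. It gives the same answer for linear onset and for late effects, and is then at least as precise. It also keeps the model small and equally spaced, which suits the autoregressive fallback. On this view the fault is a drafting conflict with low stakes: the endpoint is secondary, nothing is tested, no sample size depends on it, and dose selection rests on tolerability. Early dyspnea is also examined by the Likert responder analysis, "presented in the same manner as the primary endpoint at Hours 6, 12, and 24" (SAP 7.7.1). Finally, SAP 2.4 ties the SAP to Revised Protocol 01, which is not among the documents, so a strict comparison with the protocol is against other versions.

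Most of this limits the consequence and should be granted. It does not remove the conflict, which lies within the SAP itself: section 4.1.2 lists Hours 6 and 12 and section 7.5.2 leaves them out, with no reason given and no redaction visible there. The two grids agree only for particular profiles, and nothing in the documents says that one of those applies. The Likert analysis is a responder percentage on another scale and does not estimate the NRS AUC. If Hours 24, 48 and 72 were chosen deliberately, the endpoint definition is the text in error, and the two sections still have to be reconciled.

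**Conclusion.** The concern holds. As written, SAP 7.5.2 estimates an AUC on 0, 24, 48, 72 and not the endpoint defined in SAP 4.1.2 and protocol 8.3.2. The weights and the identity in the difference are exact once t1 is taken as Hour 0, the only reading that fits three terms. The size and direction of the error depend on the unknown early profile. In the illustrations it runs from missing an early-only effect entirely, through 13% too small and no difference, to 11% too large.

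Part I reaches 12 µg/kg/min only at Hour 8, while Part II gives fixed doses, so the discrepancy could differ between the parts. That is a possibility, not something the documents show. The harm is that a different quantity is reported under the endpoint's name. Loss of power is not the issue. This should be fixed, but it does not threaten the primary safety analysis.

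**What to change.** Before the relevant part is unblinded, amend SAP 7.5.2 to:

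- fit the repeated measures model to Hours 6, 12, 24, 48 and 72;
- state that the change at t = 0 is 0, and list the times beside the formula;
- sum i = 1 to 5 over 0, 6, 12, 24, 48, 72, with ESTIMATE coefficients 6, 9, 18, 24, 12;
- replace the autoregressive fallback, which assumes equal spacing, with a structure for unequal spacing such as spatial power on hours;
- keep the 24/48/72 version, if it was intended, only as a labelled sensitivity analysis.

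The cost is SAP wording and programming. The model does grow. Unstructured covariance parameters go from 3·4/2 = 6 to 5·6/2 = 15. Mean parameters are times × (1 + (arms − 1) + (regions − 1) + 1 baseline slope). With the SAP's three regions that is 3·5 = 15 to 5·5 = 25 in Part I, and 3·6 = 18 to 5·6 = 30 in Part II. If Japan is treated as a fourth region in Part II (an assumption; the SAP lists three), it is 3·7 = 21 to 5·7 = 35. Non-convergence, and so use of the fallback, becomes more likely, which is why the fallback should be settled in the same amendment.

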7.6 Safety

All safety presentations will be based on the Treated Subject Data Set.

7.6.1 Primary Safety Analysis

The incidence of clinically relevant hypotension from the start to 6 hours after the end of study drug infusion will be summarized by treatment. Point estimates and 95% confidence interval (CIs) for event rates will be presented by treatment, together with point estimates and 95% CIs for the risk difference and relative risk between each BMS-986231 arm and placebo. The confidence intervals will be calculated using an exact method. The 95% confidence intervals for the relative risk and risk difference will be obtained using an exact procedure that inverted the 2-sided test statistics (Agresti and Min, 2001)¹.

The event rate is calculated as the number of subjects experiencing at least one clinically relevant hypotension from the start to 6 hours after the end of study drug infusion, divided by the total number of subjects receiving study treatment.

The incidence of symptomatic hypotension up to 6 hours after the end of study drug infusion, as well as the incidence of SBP < 90 mm Hg (confirmed by a repeated measure) will be analyzed and presented in the same manner as the primary endpoint.

7.6.2 Other Safety Analyses

7.6.2.1 Deaths

All reported deaths after a subject is enrolled (i.e., has signed the informed consent) will be listed separately by subject.

Percentage of subjects who have died (all- cause and CV related) through Day 32 and Day 182, and percentage of subjects who have heart failure hospitalizations or CV mortality through Day 32 will be analyzed and presented in the same manner as the primary endpoint, respectively.

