The in-patient period will end in conjunction with the final in-patient assessment at Hour 120 or discharge, whichever comes first. All subjects enrolled as part of global part II will be followed for safety and rehospitalization endpoints through Day 32 and mortality through Day 182. Subjects in Japan who were enrolled after the end of global Part II enrollment will be followed for safety and rehospitalization endpoints through Day 32.

The start of the trial is defined as the first subject screened. End of trial is defined as the last subject's final follow-up visit on Day 182, or the last subject's scheduled procedure shown in the Time & Events schedule. For Subjects in Japan who were enrolled after the end of global Part II, The end of trial is defined as the last subject's final follow-up visit on Day 32, or the last subject's scheduled procedure shown in the Time & Events schedule.

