If investigator's use of third-party representative to assist in the follow-up portion of the study has been included in the subject's informed consent, then the investigator may use a Sponsor-retained third-party representative to assist site staff with obtaining subject's contact information or other public vital status data necessary to complete the follow-up portion of the study. The site staff and representative will consult publicly available sources, such as public health registries and databases, in order to obtain updated contact information. If after all attempts, the subject remains lost to follow-up, then the last known alive date as determined by the investigator should be reported and documented in the subject's medical records.

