6 STUDY PERIODS, TREATMENT REGIMENS AND POPULATIONS FOR ANALYSES

6.1 Study Periods

Screening period starts from 18 hours prior to start of study drug infusion to Hour 0 (the start of study drug infusion). In-hospital follow-up starts from the end of study drug infusion to Hour 120 or discharge, whichever comes first. Day 32 follow-up occurs 32 days after the start of study drug infusion. Day 182 follow-up occurs 182 days after the start of study drug infusion.

Please see the study design ([Section 2.1](#)) for the details on study periods.

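### Day 182 mortality is a crude percentage of all treated subjects, so anyone whose vital status stays unknown is in effect counted as a survivor

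*SAP*

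**What the plan says.** SAP 7.6.2.1 (Deaths) takes "Percentage of subjects who have died (all- cause and CV related) through Day 32 and Day 182" and states that these "will be analyzed and presented in the same manner as the primary endpoint, respectively". SAP 7.6.1 defines the primary-endpoint rate as subjects with at least one event, "divided by the total number of subjects receiving study treatment", and adds: "The confidence intervals will be calculated using an exact method". SAP 7.6 fixes the analysis set: "All safety presentations will be based on the Treated Subject Data Set". SAP 6.1 sets the horizon: "Day 182 follow-up occurs 182 days after the start of study drug infusion".

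The Deaths section is fully visible. It contains no time-to-event estimate, no rule for unknown vital status and no sensitivity analysis. The explicit imputation rules in the visible SAP cover only the dyspnea NRS (7.5.2) and the Likert scales (7.7.1).

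The protocol foresees incomplete follow-up. Section 3.6.1 lets a subject refuse all further contact. Section 3.6.2 defines loss to follow-up, provides for searches of public sources, and says that for a subject who remains lost "the last known alive date as determined by the investigator should be reported and documented". After the in-patient period, Table 5.1-3 schedules only a Day 32 clinic visit and a Day 182 phone call.

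**The concern.** A fixed denominator suits hypotension up to 6 hours after an in-hospital infusion, where nearly every treated subject is observed for the whole window. It transfers poorly to a 182-day endpoint whose second contact is one phone call five months after the first. There, some subjects will probably have unknown status, and the inherited rule gives them the favourable outcome.

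Mortality at Day 182 is a stated safety objective (Protocol 1.3.4, SAP 3.3). An estimator that can err only towards fewer deaths is the wrong default for a safety endpoint. If loss differs between arms, the arm with more loss looks safer for that reason alone.

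**Working it through.** **Plan figure.** The documents state no expected Day 182 mortality, loss rate or power for this endpoint, so there is nothing to reproduce. The detection probabilities in Protocol 8.1 concern hypotension and do not bear on it.

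**Step 1: what the rule does.** Split the N treated subjects into D known dead, A known alive and U unknown. The crude rate is D/N = D/(D + A + U), which is what results from setting all U alive. The true rate is (D + x)/N, with x between 0 and U. The crude rate is thus the lower bound and (D + U)/N the upper bound.

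**Step 2: size.** Assumptions, none of them from the documents: true Day 182 mortality m of 10%, 15% or 20%; constant hazard, so S(t) = (1 − m)^(t/182); a share f (5%, 10% or 15%) who drop out of sight at time L if still alive then; loss unrelated to the risk of death.

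Shortfall = f × mean of [S(L) − S(182)].

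- Loss spread evenly over 182 days: the mean of S(L) is m / (−ln(1 − m)). For m = 15% this is 0.15/0.1625 = 0.9230. Subtracting 0.85 gives 0.0730. For m = 10% and 20% the result is 0.0491 and 0.0963.
- All loss at Day 32: S(32) − S(182) = 0.0816, 0.1218 and 0.1615 for m = 10%, 15% and 20%.

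Multiplying by f gives the shortfall in percentage points:

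| m | Even loss: 5% / 10% / 15% | Loss at Day 32: 5% / 10% / 15% |
|---|---|---|
| 10% | 0.25 / 0.49 / 0.74 | 0.41 / 0.82 / 1.22 |
| 15% | 0.36 / 0.73 / 1.09 | 0.61 / 1.22 / 1.83 |
| 20% | 0.48 / 0.96 / 1.44 | 0.81 / 1.62 / 2.42 |

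The Day 32 columns matter because no contact is scheduled between Day 32 and Day 182, so last known alive dates may cluster near Day 32.

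**Step 3: the arm comparison.** With equal loss the relative risk barely moves. True rates of 10% and 20% with 10% lost evenly in each arm give crude rates of 9.51% and 19.04%: relative risk 2.00, risk difference 9.5 instead of 10 points. With unequal loss a difference appears where none exists. Take true mortality of 15% in both arms, with 5% lost on placebo and 15% on active:

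- Even loss: 14.64% against 13.91%, risk difference −0.7 points, relative risk 0.95.
- Loss at Day 32: 14.39% against 13.17%, risk difference −1.2 points, relative risk 0.92.

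**Step 4: one arm of 70** (the Part II group size), with 10 known deaths, 3 of them by Day 32, and 7 subjects lost at Day 32:

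- Crude: 10/70 = 14.3%, exact 95% CI 7.1% to 24.7%, a width of 17.6 points.
- Kaplan-Meier: 1 − (67/70) × (53/60) = 15.5%.
- Lost subjects excluded: 10/63 = 15.9%.
- All lost counted as dead: 17/70 = 24.3%.

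The crude and Kaplan-Meier figures differ by about 1 point. The two bounds differ by 10 points, and the crude table would not show this.

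**The case against.** The strongest reply is that this is a descriptive safety summary in a small Phase 2b trial. SAP 7.1 plans no significance testing, Protocol 8.4.3 asks only for a descriptive summary of deaths, and the bias is small beside the sampling error. That stands, and it limits the weight of the point.

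The protocol also works to keep unknown status rare. Subjects who stop drug stay in follow-up, public information may be used for vital status where local law allows, and deaths found that way are counted. SAP 7.3.1 tabulates non-completers and reasons by treatment through Day 182, so loss by arm will be visible. These measures reduce or reveal the problem, but none of them enters the mortality estimate.

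Kaplan-Meier is not assumption-free either. It needs non-informative censoring, and it is biased upward if registry searches add deaths among lost subjects while those not found dead are censored at last contact. Protocol 3.6.2 asks for a last known alive date only for subjects lost to follow-up, not for those who withdraw consent, and places it in the medical records without naming a CRF field. These points stand and shape the fix.

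Two stronger readings are tempting. A reader might infer that the SAP declares lost subjects to be survivors. It does not say so; the result follows from joining 7.6.2.1 to a denominator written for hypotension. The sponsor's safety conventions (SAP 8.1) and the Data Presentation Plan (SAP 9), which are not among the documents, may say more.

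A reader might also infer that late Japanese subjects will be counted as Day 182 survivors. Protocol 3.1 ends their follow-up at Day 32, and the SAP's denominator has no exception for them. But Protocol 8.4 removes them from the main global Part II Day 182 analysis, 1.3.4 limits the mortality objective to the global cohorts, and Table 5.1-3 marks the Day 182 call as not applicable to them. SAP 2.4 shows that the SAP rests on revised protocol 01, and neither its strata nor its region table includes Japan. This is an SAP that has not been updated, not a choice to count them as alive.

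**Conclusion.** The point holds as a minor estimation and reporting flaw. Under the rule as written, Day 182 mortality is the best-case bound in each arm. The understatement is about 0.25 to 1.4 points for 5-15% loss spread evenly and 10-20% true mortality, or about 0.4 to 2.4 points if loss falls at Day 32. All of these rates are assumed, as are constant hazard and loss unrelated to death; if subjects who disappear die more often, the shortfall is larger. The direction does not depend on the assumptions. Distortion of the arm comparison needs mainly unequal loss, of which the documents give no evidence. The primary hypotension conclusion is not affected.

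**What to change.** In SAP 7.6.2.1, keep the crude counts and percentages and add:

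- Kaplan-Meier all-cause mortality at Day 182 by arm, with the risk difference from placebo and its 95% CI. Censor at the last known alive date, or at last contact for subjects who withdraw consent. Apply the same vital-status ascertainment cut-off to deaths and non-deaths.
- For CV death, cumulative incidence with non-CV death as the competing event.
- The number with unknown Day 182 status by arm, with best-case and worst-case bounds, because Kaplan-Meier relies on non-informative censoring.

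Separately, bring the SAP up to the current protocol by carrying over the Protocol 8.4 exclusion of late Japanese subjects, whose details that section leaves to the SAP.

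The cost is a paragraph of SAP text and standard programming, plus a check that the last known alive or last contact date reaches the analysis database. No new visits or procedures are needed.
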